JHSPH Institutional Review Board**RESEARCH PLAN**

PI:	[name], Jhpiego		
Co-investigators in Uganda:	[name], Jhpiego Uganda [name], PREFA (Uganda) [name]. [name], Ugandan Ministry of Health [name], Jhpiego Uganda [name], PREFA	Co-Investigators in United States:	[name], Jhpiego [name], Jhpiego [name], Jhpiego [name], Jhpiego [name], AAP

Study Title: Saving Lives at Birth in Uganda: Building and Sustaining Capacity of Frontline Health Workers – A Program Evaluation**IRB No.: 5383****PI Version Number/Date:** Version 2/December 20, 2013

- Aims/objectives/research question/hypotheses:** Describe the primary and secondary aims/objectives of the research, or the project's research questions or hypotheses.

Study Aim:

The study aims are to evaluate the impact of supportive follow-up strategies for a novel twinned training and capacity-sustaining program among frontline health workers (providers) attending facility-based births in remote and district level health facilities in Uganda. The program is designed to improve provider competencies, provider performance and health outcomes among women giving birth and newborns. The goal is to reduce postpartum hemorrhage (PPH) and birth asphyxia -- leading causes of maternal and newborn mortality. Two curricula will be evaluated: Helping Mothers Survive: Bleeding After Birth (HMS: BAB) and of Helping Babies Breathe (HBB).

The objectives are presented in order of an evaluation logic model: Process, Outputs, Outcomes, and Impact.

Objectives of the Evaluation:

Objective 1 (PROCESS): Improve and sustain the frequency of **providers' practice sessions** each week of key PPH and newborn care interventions.

Objective 2 (OUTPUTS): Improve and sustain **provider competencies** during simulation training related to key PPH and newborn care practices, as measured by the percent of providers who pass, and the mean 'correct' score on the knowledge and Objective structured clinical examination (OSCE) assessments of a) HMS: BAB and b) HBB.

Objective 3 (OUTCOMES): Improve and sustain **provider performance** of routine, immediate PPH-prevention and newborn care practices for all mothers/newborns: as measured by the percent of: a) women who received oxytocin or misoprostol within 1 minute of vaginal birth, b) the percent of women among whom the placenta is inspected to standard within 15 minutes, c) the percent of newborns checked for breathing within one minute.

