2	Facility in-charge or designated provider/pharmacist	Health facility assessment checklist;	Total: 3 (Baseline, Midline, Endline)
2 and 3	Providers in health facilities who attend births on days and are present on days of training and/or assessment/observation [Population: providers who attend births]	Written knowledge tests and OSCE competency tests for BAB and HBB using simulators	Before and after BAB training Before and after HBB training day Midline assessment Endline assessment Total: 4
		Direct Clinical Observation (DCO) of births at facility	Total: 3 (Baseline, Midline, Endline); providers may be observed several times over the course of the 2 or 3 day assessments
3, 4	Women giving birth in health facilities on days of observation, and newborns [Population: women giving birth and their newborns]	Direct Clinical Observation (DCO) of births at facility	1 (women will likely be observed only with one birth over the period of the study)
4,5	All women who give birth in study facilities (and newborns) will have their service delivery statistics recorded (without identifiers) and aggregated	Abstraction from Facility registers (existing registers and supplemental information for the HMS:BAB and HBB project)	None
1, 2	Providers described above who are selected to be Peer Practice Coordinators (PPC) who attend births and are selected to be PPCs due to leadership skills [Population: see	PPC practice logs	Weekly, the PPC will record data in the practice log.

Obj.	Study Participants (Sample & Population)	Data Source	Number of Study Contacts
	above]		
1	Providers, Facility In-charges, and stakeholders such as Ministry of Health in-charges	Semi-structures interviews	1
1	Providers	Focus group discussions	1

b. Describe any screening procedures and any **inclusion or exclusion criteria**.

For Providers:

- **Inclusion Criteria:** Health providers who attend births in participating health facility and consent to be assessed at the time of enrollment and at several points in time over two years.
- **Exclusion Criteria:** none

For Peer Practice Coordinators:

- **Inclusion criteria:** criteria for being a PPC include: being an experienced skilled birth attendant and likely to remain at the facility during the study period
- **Exclusion Criteria:** Provider has <1 year of experience, and has plans to be transferred to another facility or leave the facility soon.

For Women in Labor and Delivery and Newborns - Observations of Births

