The study is a quasi-experimental design with three study arms/groups that receive different levels or intensities and modalities of the program intervention. Figure 1 (page 10) provides an overview of the intervention and evaluation components of the study. Briefly, the same simulator-based training will be provided in all three study arms. After the training, a simulator will be left in the health facility, and providers will be encouraged to practice with it regularly. In two of the study arms, specific health workers will be recruited to support the intervention by encouraging their colleagues to practice with the simulator. In one study arm, the practice will be further reinforced through mobile phone-based support. Following is a more detailed description of each of the three components.

Component 1 (Training): Training is composed of two separate training interventions. First, in each study facility, we will conduct a single day, simulator-driven training on PPH prevention and treatment; all providers who attend births will be invited to participate. Eight weeks later, in each facility, we will conduct a one-day, simulator-driven training for prevention and management of asphyxia in the newborn. After each one-day training, simulators will be left at the facility for practice with a corresponding practice schedule.

Component 2 (Peer-led Practice Sessions): On the day the first training (for PPH), 2 birth attendants at the facility will be selected to serve as peer practice coordinators (PPC). The PPCs will be trained to encourage their coworkers to participate in 15-minute practice sessions each week for 8 weeks, in which they will use the simulators to practice the skills learned in the one-day training. After the newborn asphyxia training occurs, these same PPCs will be trained to support a similar practice schedule for the following 12 weeks - 8 weeks for newborn asphyxia practice and 4 weeks for combined PPH and asphyxia skills practice.

Component 3 (Mobile phone-based support): (Note: This component is being negotiated with the ministry of health in conjunction with UNICEF due to the moratorium on mHealth interventions) Labor ward providers will be given mobile text messages for:

- 1) Content reminders
- 2) Practice reminders

[figure not shown]
PPCs will be connected to the district trainer via mobile phone for weekly phone calls during the practice periods to provide reminders and support for practice.

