 - Designated Peer Practice Coordinators (PPC) will log their weekly practice sessions on logs (full and partial arms only).
 - Data on the number of reminders that are sent to providers will be recorded, along with logs of calls between trainers and PPCs (full arm only).
 - Aggregated HMIS data related to PPH, newborn care and mortality data will be collected from routine and supplemental HMIS forms.
- When the five months of the active intervention phase is over, then there will be a midline assessment of providers and facilities: this will again involve a facility assessment, provider knowledge test and OSCEs, observation of provider performance, and qualitative data collection at some facilities. This will take place over 2 or 3 days.
- During the same time period, the research team will contact stakeholders by telephone to schedule interviews with them. Then the interviews will be conducted at the stakeholders' offices or another location, if requested by the stakeholder.
- Following the midline assessment, there will be a 'dormant' phase of no active intervention. This is to determine if competencies and performance is maintained by low-dose high-frequency practice in the absence of donor support. We will return six months later for an endline assessment, which is the same as the midline assessment except there will be no qualitative component.

Table 7. – Description of Data Collection Instruments

Tool #	Title	Content
1	Health Worker Listing	Name and cadre for each health worker at each facility. This will be used to generate a unique ID for each provider
2	Facility Inventory	Information about the tools and equipment available at the facility related to the study intervention, such as the availability of uterotonic drugs and neonatal resuscitators.
3	Direct clinical observation tool	Structured checklist that observers will use to take notes on the care provided to women and neonates, including routine care and treatment for postpartum hemorrhage or neonatal asphyxia.
4	Supplemental maternity register	Note: We will provide this register to facilities, but Jhpiego researchers will not abstract individual records from this document (facility staff will do this). This register collects data about each birth that is relevant to this study, such as whether a woman was diagnosed with postpartum hemorrhage and whether a newborn received bag & mask resuscitation.

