5	Supplemental monthly summary report	This aggregated monthly form collects facility-level indicators related to this study, such as the number of women diagnosed with postpartum hemorrhage and the proportion of those women treated with oxytocin or misoprostol.
6	Participant Characteristics – Baseline	This self-administered questionnaire collects information about qualifications of training participants and their prior experience and confidence related to preventing and treating postpartum hemorrhage and neonatal asphyxia.
7	Knowledge Test: Bleeding	15 multiple choice questions that test providers' knowledge of the

Tool #	Title	Content
	after Birth	content taught in the Bleeding After Birth training.
8a-c	Observed Structured Clinical Examinations (OSCEs): Bleeding After Birth	Structured checklists that trainers will use to examine providers' skills related to routine care for third stage labor, retained placenta, and severe hemorrhage due to atony. Providers will demonstrate skills on a simulator.
9	Peer Practice Coordinators' Practice Log	In two of the study arms, peer practice coordinators will use this form to record when the providers at their facility practice with the simulator and the topic that they practice.
10	Phone Support for Peer Practice Coordinators	This will log the data and content of the weekly phone support that trainers have with peer practice coordinators (in one study arm only.)
11	Opt-in Sheet for Mobile Phone Reminders for Providers and PPCs	In one study arm, providers will have the option of receiving reminders about training content via their personal mobile phones.
12	Knowledge Test: Helping Babies Breathe	17 multiple choice questions related to the content taught in the Helping Babies Breathe training.
13 a, b	OSCEs: Helping Babies Breathe	Structured checklists that trainers will use to examine providers' skills related to neonatal resuscitation using stimulation and ventilation equipment. Providers will demonstrate skills on a simulator.
	Qualitative	
14	Focus group discussion guide	Health care providers will be asked about their experiences with the program, particularly what the factors that motivated or discouraged them from practicing with the simulator.
15	Semi-structured interview guide: Health facility in-charges	Health facility in-charges will be asked about their experiences implementing the program and for their opinions about how to strengthen and sustain it.

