The primary independent variable will be the study group represented as 2 indicator variables for full and partial training package with training-only as the reference group. For these hypotheses, we will only use endline data. Additional variables, related to provider- and facility characteristics predictive of these outcomes, such as cadre, number of years of provider's experience, and number of prior births attended in last 90 days, will be also included in the model. Analysis of residuals will inform whether the assumptions of the generalized linear model, such as normality and homoscedasticity of residuals as well as linear fit, are satisfied.

Additional analyses will include:

1. At baseline, midline and endline we will collect data from **all study facilities** consisting of service delivery statistics, and facility inventory. These data will be analyzed using population-average marginal generalized linear models estimated using generalized estimating equations (GEE) with exchangeable working correlation structure to account for repeated observations within facilities. The dependent variable will be service delivery statistics. The independent variables will include time (represented as 2 indicator variables for midline and endline with baseline as the reference group), study group (represented as 2 indicator variables for full and partial training groups with training-only as the reference group), and interaction terms (study group by time). The interaction terms will be examined to assess whether there are differences between study groups that change significantly over time.
2. Providers who are trained will keep **logs of their practice sessions**. This is process evaluation data. These data (for example on number of times a scenario is practiced) will be compared across the three study groups using generalized linear models with Poisson or Negative Binomial distribution for the outcome.
3. **Routinely collected data from health facility registers** (recorded daily but aggregated monthly) on services provided to clients and health outcomes (discharge, or deaths and stillbirths) will be analyzed using longitudinal data analysis to account for repeated observations at each facility. This will be for population-averaged marginal generalized linear models using generalized estimating equations (GEE) and exchangeable working correlation structure.

Qualitative Analysis

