	
Other (describe):
 
Providers' identifiers will be collected but not kept with the study data (kept separate) for all data sources except the logbooks of provider practice, log of telephone contacts between trainers and peer practice coordinators, and the list of names and telephone numbers of providers that opt in for receiving SMS messages related to the training. Logbooks that record practice sessions that will include health care providers' names will be kept in the simulator case in the possession of the PPCs. For all other data sources, hard copies of data collection materials will be kept locked in a secure cabinet or room with limited access by specified individuals. COPIES WILL BE KEPT IN INVESTIGATOR'S POSSESSION DURING TRANSPORT. When possible, redacted (de-identified) versions of the data collection sheets will be used for coding and analysis.
 
Women's identifiers will not be collected on paper at all.

B. Electronic Databases:	

Note: This refers to the initial database into which study data is entered and stored. If this "Study Database" includes personal identifiers from participants, only de-identified analytic datasets should be used for data analysis except in instances in which identifying information is required. Databases that retain identifying information require a higher degree of electronic security.
	
	The study collects data that are anonymous; no personal identifiers will be recorded or retained from any study participants in either direct or coded form.
	Personal identifiers are included in the database. If breach of confidentiality poses more than minimal risk to participants because data are personally sensitive in nature (for example, involve substance abuse, mental health, genetic propensities, sexual practices or activities), access to identifiers will be restricted. These data are stored on a secure server protected by strong password, and will be only accessible by authorized study personnel. Data will be coded when

	possible. Identifiable data transferred or stored via portable electronic devices (e.g., laptops, flashdrives) will be encrypted. The devices on which this information is stored are accessible only to individuals who need access to these data.

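### Practice sessions are counted only in coordinators' logs from two arms: a full-versus-partial difference could partly be fuller recording, and the planned three-group comparison has no training-only data

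*Combined protocol and SAP*

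**What the plan says.** Section 1 puts practice first among the objectives: "Objective 1 (PROCESS): Improve and sustain the frequency of" weekly practice sessions.

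The count comes from one instrument. Section 4b2 (Times of Data Collection) states: "Designated Peer Practice Coordinators (PPC) will log their weekly practice sessions on logs (full and partial arms only". Table 7 describes Tool 9 in the same way: "peer practice coordinators will use this form to record when the providers at their facility practice with the simulator". Table 2 adds: "Weekly, the PPC will record data in the practice log". Under section 5b, the practice logbooks "will be kept in the simulator case in the possession of the PPCs".

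Trainer contact differs by arm. Section 4b1 (Component 3) links full-arm coordinators to the district trainer "for weekly phone calls during the practice periods to provide reminders and support for practice". Tool 10 records these calls, in that arm only. The intervention description in 4b2 adds that trainers will use the mobile link to assess coordinators remotely. Full-arm providers are also offered text reminders to practise.

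Section 4b5 (Additional analyses, item 2) gives the analysis: "These data (for example on number of times a scenario is practiced) will be compared" across all three study groups, by Poisson or negative binomial regression. That item says trained providers keep the logs, whereas Table 2, section 4b2 and Tool 9 give the task to coordinators.

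The text available describes no second count, log audit or completeness check. The focus groups and interviews that also serve Objective 1 ask about experience and motivation.

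**The concern.** The person who fills in the log is the person responsible for getting colleagues to practise. The component that separates the full from the partial arm is regular outside contact with that person about that task. Such contact is meant to raise practice, but it may also make the coordinator write sessions down more faithfully. A log count alone cannot tell these apart.

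Section 4b2 presents the full-versus-partial contrast as a test of what mobile support adds. Practice level is also used in the planned correlation with test scores and observed performance (section 3c), in the secondary outcome on factors associated with frequent practice (4b5), and in the high/low adherence grouping for the qualitative work (Table 6 and the doer/non-doer analysis).

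Separately, the model in 4b5 item 2 calls for a training-only group that the data collection does not supply.

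**Working it through.** **1. What each arm supplies** (Table 1, section 4b2, Table 7)

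| Arm | Coordinator | Practice log | Weekly trainer calls |
|---|---|---|---|
| Training-only | no | no | no |
| Partial | yes | yes | no |
| Full | yes | yes | yes |

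Full versus partial is the only contrast the logs can support, and within it the calls vary exactly with arm.

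**2. What the logged ratio estimates.** Let *t* be the true session rate and *c* the fraction of sessions recorded. The logged rate is *t* × *c*, so

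logged ratio = (t_full / t_partial) × (c_full / c_partial).

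If true practice is equal, the logged ratio is c_full / c_partial. The plan gives no value for *c*, so one observed ratio cannot separate the two factors.

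**3. Illustration.** There is no figure in the plan to reproduce. Inputs from the plan: 8 + 12 = 20 practice weeks (4b1, Component 2) and 133 facilities (section 3). Assumptions: an even split (133/3 = 44.3 facilities per arm), one true session per facility-week in both arms, the completeness values below, and negative binomial dispersion k of 0 (Poisson) or 0.3. District clustering is ignored.

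Mean logged sessions per facility: m = 20c. 
SE of the log ratio = √{[(1/m_partial + k) + (1/m_full + k)] / 44.3}. 
Chance of a nominally significant result in favour of full (two-sided 0.05) = Φ(ln ratio / SE − 1.96).

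For 70% versus 85%: m = 14 and 17, ratio = 17/14 = 1.21, ln = 0.194. With k = 0, SE = 0.054, z = 3.58 and the chance is 95%. With k = 0.3, SE = 0.128, z = 1.51 and the chance is 33%.

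| Recorded, partial / full | Logged ratio | Chance, k = 0 | Chance, k = 0.3 |
|---|---|---|---|
| 90% / 95% | 1.06 | 19% | 6% |
| 80% / 90% | 1.13 | 63% | 15% |
| 70% / 85% | 1.21 | 95% | 33% |
| 60% / 90% | 1.50 | >99% | 88% |

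**4. Counting per provider instead.** 651/133 = 4.9 providers per facility (Table 3 and section 3), so 44 × 4.9 × 20 = 4,312 provider-weeks per arm. Assume one true session per provider-week.

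- 75% versus 90% recorded: 3,234 and 3,881 sessions, ratio 1.20, SE = √(1/3,881 + 1/3,234) = 0.0238, z = 7.7. With an assumed design effect of 10, z = 7.7/√10 = 2.4.
- 80% versus 90% recorded: z = 5.0, falling to 1.6.
- With k = 0.3 and about 81 logged sessions per facility (4.9 × 20 × 0.825), variance rises by 1 + 0.3 × 81 ≈ 25. The 1.20 ratio then gives z ≈ 7.7/5 = 1.5.

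A recording gap moves the estimated ratio whatever the dispersion. Whether it would also reach significance depends on assumptions the plan cannot settle.

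**The case against.** The strongest reply is that the mechanism is inferred. The calls are described as reminding and supporting coordinators about practice. Nothing says that trainers ask for, check or prompt the log. Both arms use the same form, and section 8a makes the log the coordinator's own tool for seeing who has practised, which gives partial-arm coordinators a reason to keep it too. This stands: differential recording is a possibility, and the remote assessment mentioned in 4b2 makes it more plausible without establishing it.

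Second, this is a process measure listed under additional analyses. That also stands. A reader might infer that the trial's main conclusions are at risk, but the documents do not support this. The oxytocin outcome is taken from direct clinical observation, and the newborn outcome is listed among the observed-care measures (Objective 4). Competencies come from knowledge tests and OSCEs, and none of Hypotheses 1 to 4 compares full with partial.

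Third, recall is also self-report. Providers are unblinded, those in the full arm are offered practice reminders, four weeks is a fraction of a 20-week programme, and absent providers are missed. This rules out replacing the prospective log with recall. It does not rule out a second count not written by the coordinator, and it leaves the training-only gap unanswered.

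Finally, the focus groups and interviews might reveal under-logging, but they cover at most 24 purposively chosen facilities, at midline, with no session count described. The oversight text under section 17 was not available for this check, so an audit described there cannot be excluded.

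**Conclusion.** The point holds in a limited form. A full-versus-partial difference in logged sessions could partly reflect fuller recording, and the plan has no means of checking. The three-group log comparison cannot be run as written, because one group has no logs.

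A reader might go further and conclude that the calls do inflate recording, or that a false positive is likely. The documents do not support either. They say nothing on completeness or dispersion. The assumed scenarios give logged ratios from 1.06 to 1.50, with a chance of nominal significance from 6% to over 99%. All of them assume better recording in the full arm; the reverse would hide a true gain.

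What is affected is Objective 1, the reading of what mobile support adds to practice, and the secondary uses of practice level. The asymmetry arises only if Component 3 is delivered, and section 4b1 notes that it was still being negotiated. This is an inexpensive improvement worth making, not a threat to the primary results.

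**What to change.** At the midline and endline provider assessments, have the external data collectors ask every provider, in the same words in all arms, how many simulator sessions they took part in over the last four weeks and the date of the last one.

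In section 4b5, Additional analyses, item 2:

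- use this item for the three-group comparison;
- restrict the log comparison to full versus partial, and state who keeps the logs;
- at midline, report the ratio of logged to provider-reported sessions by arm for the overlapping weeks, limited to the providers interviewed (the log is by name, so this is possible);
- read a full-versus-partial log difference as more practice only if both measures agree.

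The endline answers also describe practice in the dormant phase, whereas section 4b2 places logging in the active phase.

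The cost is about a minute per provider at visits already planned, plus a few lines of analysis text. The recall is unblinded, covers only four weeks and reaches only providers present that day, so it supplements the logs. It would not help choose the high- and low-adherence facilities for the qualitative work, which is itself done at midline.
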